ISOMETRIC CORE MUSCLE ENDURANCE IN HEALTHY ACTIVE AND NON-
ACTIVE WORKING AGE POPULATIONS
[name], [name]

28.05.2018

ISOMETRIC CORE MUSCLE ENDURANCE IN HEALTHY ACTIVE AND NON-ACTIVE WORKING AGE POPULATIONS

[name], [name]

This is the first study to investigate the core muscle endurance of different age groups and genders with all four endurance tests of the core.

Core endurance has been previously tested in literature with either isometric or dynamic tests. Strand et al. (1), however, claim that dynamic tests like sit-ups are more indicative of inner range muscle strength and power, and therefore, do not reflect the muscle endurance. Biering-Sorensen, McGill v-sit and side plank have been found to be the most reliable and safe in a myriad of different isometric core endurance tests (2–7). The reliability of v-sit has been found to be 0.66-0.73 (7–9), Biering-Sorensen 0.54-0.99 (5,7,9) right side plank (RSP) 0.74-0.78 and left side plank (LSP) 0.91-0.96 (7,8) in healthy adult populations with and without low back pain (LBP).

Core endurance may be affected by different factors. Correia et al. (10) found that core muscle activity of people who experience LBP is delayed, which may lead to further dysfunction and pain. It is unclear, though, if reduced core muscle endurance affects LBP experience or the risk of its' development.

Another possible factor influencing the core muscle endurance is age. However, the results in the older general population are contradicting (mean age values of 37–47.95) (11,12) due to possible influence of participants' lifestyle, work, and selected endurance tests. We are living in an aging society and further investigation should be carried out to reject or confirm this possible connection.

As a result of aging, a healthy person loses 1–2% of the muscle mass (13–15) and put on 0.45kg fat every year after reaching the age of 40 (16,17). An increase in BMI has been associated with reduced core muscle endurance (18-20). However, physical activity may reduce these changes and account for different results of previous studies.

The purpose of this study was to investigate a possible correlation between core muscle endurance and participants' age in healthy adult population. The secondary purpose was to identify other dependent variables influencing isometric core muscle endurance (e.g. low back pain, physical activity, gender, body mass index).

48 (35 females, 13 males) healthy adults (aged 21–66 years) will perform 4 isometric core muscle endurance tests- Biering-Sorensen, McGill V-sit, right and left side plank. All

participants will be divided into 2 age groups considering the physiological changes taking place during aging- <41 and >40.

Guidelines suggest that to maintain a healthy lifestyle, adults aged between 18 and 65 should do moderate-intensity aerobic physical activities for a minimum of 30 minutes, 5 times a week, or high-intensity aerobic activities 20 minutes, 3 times a week (21–24). Participants will also be divided based on the physical activity level- groups that meets national and international guidelines and a group that doesn't. A correlation between core endurance and age, gender, low back pain (LBP), physical activity level (PAL), and body mass index (BMI) is calculated using Pearson's correlation and Independent T-test on SPSS. It is a case control study, collecting both numerical and categorical data.

Reference list

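### Does the plan leave open whether age in years or the <41 / >40 split answers the primary age question?

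*Combined protocol and SAP*

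**What the plan says.** The document has no numbered sections. Three places bear on the point.

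- **Opening statement and purpose (introduction).** The study is introduced as one of the "core muscle endurance of different age groups and genders". The purpose is to "investigate a possible correlation between core muscle endurance and" participants' age. A second aim follows: "The secondary purpose was to identify other dependent variables influencing isometric core muscle endurance", with low back pain, physical activity, gender and BMI as examples.
- **Groupings (methods paragraph).** It states that "participants will be divided into 2 age groups considering the physiological changes taking place during aging- <41 and >40". It continues: "Participants will also be divided based on the physical activity level", according to whether guidelines are met.
- **Analysis (methods paragraph).** One sentence lists age, gender, low back pain, activity level and BMI, and says that a correlation with core endurance is calculated using Pearson's "correlation and Independent T-test on SPSS". The next sentence describes the study as "collecting both numerical and categorical data".

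No sentence pairs a test with a factor or states what the two age groups are for. The rest of the document is the reference list.

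**The concern.** Age appears in two forms, years and two groups, and two tests are named that could each be applied to it. Read strictly, the plan permits Pearson on years, a t-test between groups, or both without ranking.

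Two consequences would follow on the primary question. If both were run and either could be claimed, the false-positive rate would exceed its nominal level. If only the group comparison were used, splitting age at 40 would discard information and power unless endurance really falls in a step there. Both would apply to each of the four endurance tests.

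**Working it through.** **Does the text point to one reading?** The purpose names a correlation with age, not with age group. The analysis sentence names Pearson first and the t-test second, and the data are said to be numerical and categorical. Matching these gives Pearson for age and BMI, and the t-test for two-group factors.

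Three phrases seem to point the other way, but none is strong.

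- The word correlation also covers gender. This is loose wording, but Pearson's r on a 0/1 variable gives the same p-value as the equal-variance t-test. It says nothing about how age is coded.
- The reference to age groups in the opening statement is a claim of novelty, not a method.
- The word also, before the activity grouping, shows that two groupings exist. It does not show that the age grouping decides the primary question.

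**How much could the choice matter?** From the plan: 35 + 13 = 48 people, aged 21-66, cut between 40 and 41. The plan gives no alpha, power, effect size or age distribution, so there is no planned figure to reproduce. Assumed: two-sided alpha 0.05, whole-year ages uniform over 21-66, a linear effect and normal scores.

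*Information kept by the split* is the squared correlation between age and the over-40 indicator.

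- There are 46 possible ages, with variance (46² − 1)/12 = 176.25.
- Ages 21-40: 20 values, mean 30.5. Ages 41-66: 26 values, mean 53.5. Difference 23.
- p(1 − p) = (26/46)(20/46) = 0.2457.
- 23² × 0.2457 / 176.25 = 0.738, so 26% is lost. 48 × 0.738 = 35.4 people.

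*Significance rates* (400,000 simulated studies at r = 0, 200,000 at each other r), in % of studies for one endurance test. The last two columns are differences: either minus Pearson, and either minus t-test.

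| True r | Pearson | t-test | Either | t-test only | Pearson only |
|---|---|---|---|---|---|
| 0 | 5.0 | 5.0 | 7.4 | 2.4 | 2.4 |
| 0.2 | 27.7 | 21.5 | 32.0 | 4.3 | 10.5 |
| 0.3 | 55.9 | 43.2 | 59.9 | 4.0 | 16.7 |
| 0.4 | 82.7 | 69.1 | 84.9 | 2.2 | 15.8 |
| 0.5 | 96.8 | 89.3 | 97.3 | 0.5 | 8.0 |

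At r = 0.3 the verdicts differ in 4.0 + 16.7 = 20.7% of studies. In 16.7/20.7 = 81% of those, Pearson is significant and the t-test is not. If Pearson leads, these cases do no harm. What remains is the t-test-only column, about 2 to 4 points up to r = 0.4. The two tests pointed in opposite directions, with either significant, in at most 0.005% of studies.

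*Sensitivity to the age distribution.* Over nine shapes, the either-test rate at r = 0 was 6.3% to 8.5%, an excess of 1.3 to 3.5 points over 5%. The peak rate of differing verdicts ran from 10% (two well-separated age clusters) to 36% (only 14% of people over 40).

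*If the true effect is a step at 40* (r = 0.40), the t-test has 83% power and Pearson 69%.

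**The case for a change.** The strongest contrary argument is that the ordinary reading leaves the age groups with no stated use. The cut is justified by the physiology of aging, and the introduction describes bodily changes after age 40, so the split looks like a substantive contrast and not just a table layout. Two competent analysts could therefore report different primary age results, both within the plan. At r = 0.3 to 0.4 the verdict would differ in roughly one study in five, and the split costs more power if ages are closer to normal: with a 24/24 split, an approximate formula gives 60% against 81% at r = 0.4. A single sentence would settle it cheaply.

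Part of this stands. The role of the groups is not stated, and a labelled role would be tidier. The rest weakens on inspection. A physiological reason for looking at people over 40 supports a supplementary comparison, which is also the more powerful one if a step exists. It does not displace the correlation that the purpose names. The one-in-five figure counts mostly studies in which Pearson alone is significant, which is a problem only if the t-test governs. The 7.4% error rate needs a rule that either result may be claimed, and the plan states no such rule.

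The price is also less certain than it looks. The purpose is written in the past tense and the methods give an exact sex split. If the data were already in hand, a new sentence would not be prespecification. The document does not settle this.

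**Conclusion.** This is a gap that analysts fill sensibly, and no change to the plan follows. The purpose, the named method and the type of variable together point to Pearson's correlation with age in years. The <41 / >40 comparison then stands beside it as a description, or as a check for a step. Writing that down would select a method already in the plan and would not alter the primary result.

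The exposure that remains is small: about 2 to 4 percentage points per endurance test for true correlations from 0 to 0.4, and only if a t-test positive were claimed where Pearson is negative. The 26% loss of information arises only if the t-test replaced the correlation, which the purpose makes unlikely. These figures rest on uniform ages over 21-66, a linear effect, normal scores and two-sided alpha 0.05. None of these is given in the plan, and the size moves with the age distribution as shown above.

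### The plan tests each factor alone, so age may stand in for sex or activity, and the related secondary factors cannot be told apart

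*Combined protocol and SAP*

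**What the plan says.** The analysis plan is one sentence in the unnumbered methods paragraph: "A correlation between core endurance and age, gender, low back pain (LBP), physical activity level (PAL), and body mass index (BMI) is calculated using" two methods. The sentence ends by naming them as Pearson's "correlation and Independent T-test on SPSS". The sample is described as follows: "48 (35 females, 13 males) healthy adults (aged 21–66 years) will perform 4 isometric core muscle endurance tests". Participants are split into two age groups at 40 and, separately, by whether they meet physical activity guidelines. Nothing is said about balancing sex or activity across the age groups, and no regression, partial correlation, ANCOVA, stratified or matched analysis is mentioned.

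The purpose paragraph sets the primary aim, to "investigate a possible correlation between core muscle endurance and participants' age in healthy adult population", and then adds: "The secondary purpose was to identify other dependent variables influencing isometric core muscle endurance". It names low back pain, activity, gender and BMI.

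The background links these factors to one another. It describes fat gain with age, then says: "An increase in BMI has been associated with reduced core muscle endurance". It goes on: "However, physical activity may reduce these changes and account for different results of previous studies". On low back pain it says: "It is unclear, though, if reduced core muscle endurance affects LBP experience".

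**The concern.** A Pearson correlation or a two-sample t-test cannot hold a third factor constant. The sample is not randomised, so people of different ages may also differ in sex mix or activity. A crude age association could then partly reflect that mix, or be masked by it. The background raises this explanation for the conflict between earlier studies, yet the planned age analysis leaves activity out even though the study records it. The result would carry the same ambiguity.

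The secondary aim is more directly affected. It asks which factors influence endurance, and the background expects activity, BMI and age to go together. With one-at-a-time tests, a factor with no association of its own can appear to matter because it is related to one that does.

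**Working it through.** **Inputs from the documents.** n = 48 (35 + 13 = 48), five factors, four endurance tests, two age groups. The documents give no significance level, power, effect size, SD, or distribution of sex or activity by age, so there is no planned figure to reproduce.

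**Assumed throughout.** Two-sided 5% tests, normal errors, and the effect sizes shown. Rejection rates come from simulation (20,000 to 40,000 datasets per scenario). They show what could happen, and do not estimate the bias in this study.

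**1. One pure confounder C, no age effect.** The crude age correlation equals r(age, C) × r(C, endurance).

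| r(age, C) / r(C, endurance) | Crude r | Crude test rejects | Adjusted test rejects |
|---|---|---|---|
| 0.2 / 0.3 | 0.06 | 7% | 5% |
| 0.3 / 0.3 | 0.09 | 9% | 5% |
| 0.4 / 0.4 | 0.16 | about 19% | 5% |
| 0.5 / 0.5 | 0.25 | 41% | 5% |

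**2. Sex.** Assume 24 people per age group, a sex difference of 0.8 SD and no age effect. The shift in the age-group difference is 0.8 × (difference in number of men) / 24.

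| Men by age group | Shift (SD) | Crude t-test rejects | Adjusted test rejects |
|---|---|---|---|
| 8 v 5 | 0.8 × 3/24 = 0.10 | 5% | 5% |
| 9 v 4 | 0.8 × 5/24 = 0.17 | 7% | 5% |
| 10 v 3 | 0.8 × 7/24 = 0.23 | 10% | 5% |

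If sex is unrelated to age group, the hypergeometric probability of a split at least as uneven as 10 v 3 (in either direction) is 0.049. The probability of 8 v 5 or more even is 0.81.

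**3. Activity.** Assume a yes/no factor worth 0.8 SD, with 37% of one age half and 63% of the other active (latent correlation with age of 0.4). Slopes are per SD of age.

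| True age slope | More active half | Crude slope | Crude detects | Adjusted detects |
|---|---|---|---|---|
| -0.40 | Older | -0.27 | 40% | 70% |
| -0.40 | Younger | -0.53 | 90% | 70% |
| 0 | Younger | -0.13 | 12% | 5% |

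With a weaker latent correlation of 0.2, the younger half more active and no age effect, the crude test rejects about 7%.

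**4. Secondary aim.** Let BMI have no effect of its own but be related to activity, which does have one. With both correlations (activity-BMI and activity-endurance) at 0.3, 0.4 or 0.5, the crude BMI test rejects 9%, 20% or 41%, against 5% when activity is in the model.

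**5. Cost of adjusting.** The standard error of the age slope changes by sqrt((1 − R²) × 46/df), before collinearity, where R² is the share of variance the covariates explain.

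- Age, sex and activity, df 44: 1.022 at R² = 0; 0.915 at R² = 0.2.
- All five factors, df 42: 1.047 at R² = 0; 0.936 at R² = 0.2.

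The smallest correlation detectable with 80% power is tanh((1.960 + 0.842)/sqrt(45 − k)), with k covariates: 0.395 for k = 0, 0.403 for k = 2 and 0.412 for k = 4.

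**The case against.** The strongest reply is that the primary aim is worded as a correlation, and Pearson's r estimates exactly that. This stands: the crude result is valid description and should be kept. Confounding matters only once the result is read as an effect of age itself. The reply does not rescue the secondary aim, which speaks of influence.

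Second, no bias has been shown. If sex is unrelated to age group, the crude test averaged over chance splits rejects about 5%, so sex inflates false positives only if recruitment makes it differ by age. The activity contrast also depends on an unknown direction: one mix hides a true age effect and the other exaggerates it. Both points are right. They limit how much can be claimed, but they do not tell a reader which case applies to these 48 people; an adjusted result beside the crude one would show how much the answer moves.

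Third, activity may be a mediator. If people become less active as they age, the crude association is a real total effect and adjustment removes part of it. That is also correct, and it is why both results are needed. The background sentence on activity can also be read as effect modification, which an additive model does not address.

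Fourth, more models mean more coefficients. The plan already implies 5 × 4 = 20 factor-by-test comparisons, and adjustment does not settle how those should be handled.

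**Conclusion.** The concern holds and should be fixed; it is not fatal. The plan contains only one-factor methods, and its own background gives reasons to expect the factors to be related. The age result can stand as a crude association but cannot resolve the question the background raises. The secondary aim cannot be met by the planned tests if the factors are related.

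The size is unknown. Under the assumed scenarios the crude age test's false-positive rate runs from nominal to 41%, with the upper end requiring correlations of 0.5/0.5 that the documents do not support or exclude. A true slope can be understated or overstated by about a third (-0.27 or -0.53 for -0.40). Reading these as errors assumes that the third factor is a confounder and not a step on the path from age to endurance.

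**What to change.** For each of the four endurance tests, pre-specify:

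1. The crude age correlation, as now planned.
2. A linear regression on age in years, sex and activity group, reporting the age slope with a 95% CI.
3. The same model with BMI and low back pain added. Report the age slope again, and read the secondary factors from this model as adjusted associations, not causes.

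BMI and low back pain stay out of the first model because BMI may lie on the path from age to endurance, and low back pain may follow from low endurance. In the second case, adjusting for it pulls the age slope toward zero: from -0.30 to between -0.29 and -0.16 in simulations assuming 30% prevalence and a range of strengths. Keep the t-tests as unadjusted description. An age-by-activity term can be shown as exploratory; 48 people give it little precision.

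The cost is about two sentences of analysis text and a standard SPSS procedure, with no new data or participants. Residual degrees of freedom fall from 46 to 44 and 42. Three limits should be stated: the first model removes part of the total age effect if activity changes with age; adjustment does not prove cause; and work, which the background mentions, is not among the analysed factors and so cannot be adjusted for.

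### Must the plan say whether its t-test pools the variances, given 35 women and 13 men?

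*Combined protocol and SAP*

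**What the plan says.** The whole analysis plan is one sentence in the unnumbered methods paragraph. It lists age, gender, low back pain, physical activity level and BMI as the factors to be related to endurance, and gives the methods as Pearson's "correlation and Independent T-test on SPSS". It does not pair factors with methods and does not state the form of the t-test, a significance level or the scale of the outcome.

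The same paragraph fixes the sample as "48 (35 females, 13 males) healthy adults" and the outcomes as "4 isometric core muscle endurance tests- Biering-Sorensen, McGill V-sit, right and left side plank". Two further splits are planned, with no group sizes given: "participants will be divided into 2 age groups" and "Participants will also be divided based on the physical activity level".

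The purpose paragraph makes age the main question. Gender, low back pain, activity and BMI come under the next aim: "The secondary purpose was to identify other dependent variables influencing isometric core muscle endurance".

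**The concern.** The pooled t-test assumes equal SDs, and with unequal groups it loses its level when they are not equal. If the smaller group is the more variable, the standard error is too small and false positives rise. If it is the less variable, the test is conservative. The sex split is known in advance and is uneven (35/13 = 2.7 to 1), so the sex comparison is exposed in a way that a balanced one would not be.

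The wording also leaves the choice open. Sex could be analysed by the pooled test, by Welch, by a form picked after Levene's test, or by a Pearson correlation with sex coded 0/1, which gives exactly the pooled p-value. At stake are the p-values and confidence intervals for the sex difference on four outcomes and, if their groups are also uneven, those for age group and activity level.

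**Working it through.** **Inputs.** From the methods paragraph: 35 women and 13 men (35 + 13 = 48, which agrees with the stated total). The plan gives no alpha, power, effect size or SD, so there is no sample-size figure to reproduce. Assumed: two-sided 5%, and a male/female SD ratio r from 0.5 to 2.

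**Why the ratio matters.** Take the female SD as 1. The pooled test estimates the variance of the mean difference, on average, as

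V_pooled = [(34 + 12r²)/46] × (1/35 + 1/13),

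whereas the true variance is V_true = 1/35 + r²/13. The type I error is roughly the two-sided normal tail area beyond t(0.975, 46 df) × √(V_pooled/V_true), with t = 2.013.

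- r = 2: V_pooled = (82/46) × 0.1055 = 0.1881; V_true = 0.0286 + 0.3077 = 0.3363; √(0.1881/0.3363) = 0.748; cut-off 1.505; error about 13.2%.
- r = 0.5: V_pooled = (37/46) × 0.1055 = 0.0849; V_true = 0.0286 + 0.0192 = 0.0478; √(0.0849/0.0478) = 1.332; cut-off 2.682; error about 0.7%.

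**Simulation on normal data**, equal means, 200,000 runs per setting, type I error in %:

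| SD ratio (male/female) | Pooled | Welch | Form chosen by Levene |
|---|---|---|---|
| 0.5 | 1.1 | 5.0 | 4.1 |
| 0.67 | 2.1 | 5.0 | 3.5 |
| 1 | 5.0 | 5.1 | 5.1 |
| 1.25 | 7.6 | 5.1 | 6.9 |
| 1.5 | 10.0 | 5.1 | 7.6 |
| 2 | 14.2 | 5.0 | 6.7 |

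The mechanism is real, and it comes from the imbalance: at 24 versus 24 the pooled test gives 5.1% at ratio 1.5 and 5.3% at ratio 2.

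**Cost of Welch if the SDs are equal.** At a difference of 0.93 SD, power is 78.1% against 80.2% for the pooled test, a loss of about 2 points.

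**Skewed hold times**, log-normal, 13 versus 35:

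- Identical groups, CV 0.3, 0.5, 0.7 and 0.9: pooled 4.9, 4.9, 4.7 and 4.5%; Welch 5.2, 5.5, 5.7 and 6.0%. Here Welch is slightly liberal.
- Male mean 1.5 times female, common CV 0.3, 0.5 and 0.7, non-coverage of the 95% interval: pooled 10.1, 10.0 and 9.8%; Welch 5.6, 6.4 and 7.3%; Levene-chosen 7.3, 6.9 and 6.5%.
- Male mean 1.25 times female, CV 0.7: Welch 6.7%, Levene-chosen 5.0%.
- Equal means, female CV 0.5, SD ratio 2 (so the male CV is 1.0): pooled 13.9%, Welch 10.2%, Levene-chosen 10.3%.

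Welch beats the pooled form where the SDs differ in the harmful direction, but it does not restore 5%, and it does not always beat selection by Levene's test.

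**Other splits.** For SD ratios (smaller/larger group) from 0.5 to 2, pooled error is about 5.1–5.2% at 24/24, 3.2–7.9% at 20/28, 1.8–11.2% at 16/32 and 0.6–17.7% at 10/38. Since the plan does not give the age-group and activity-group sizes, these figures cannot be tied to those comparisons.

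**The case for a change.** The best case for a change is that it is cheap. One sentence naming Welch and its 95% interval needs no new data, holds the level on normal data at the split the plan already fixes, and settles which result is reported. The plan calls the analysis of all five factors a correlation, so a 0/1-coded Pearson for sex, and hence the pooled test, is a literal reading. An open choice could also be abused: reporting the smaller of the two p-values gives 6.2% with equal SDs and 14.2% at ratio 2 on normal data.

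Much of this stands as advice. It falls short of showing a fault, for four reasons.

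- The inflation needs the pooled form and a more variable male group together, and the documents establish neither.
- The plan says it collects both numerical and categorical data and names two methods. The natural pairing is Pearson for age in years and BMI, and the t-test for two-group factors.
- Nothing in the plan points to picking the smaller p-value. At SD ratios of 0.5 and 0.67 that practice gives 4.9% and 5.1%, so its harm is confined to ratios of 1 or more.
- Any rule fixed in advance removes the choice between results. What favours Welch in particular is its behaviour on normal data, and the documents do not establish normality.

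An added analysis of log hold time would estimate a ratio of geometric means, which is a different quantity, and would put a second result beside every comparison on four outcomes. It is an option, not a repair.

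**Conclusion.** No change is needed. The plan leaves out the form of the t-test, and an analyst can fill that gap sensibly within the existing wording. For the sex comparison the pooled form would have a type I error of about 1% to 14% at SD ratios from 0.5 to 2, assuming normal data and a two-sided 5% level. With equal SDs it is 5.0%, against 5.1% for Welch. The documents give no SDs, so where the trial lies in that range is unknown.

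The numerical case covers sex only, because no other group sizes are stated. It concerns secondary comparisons and does not reach the primary Pearson correlation with age. Naming Welch in advance would be a sound optional clarification, costing about 2 points of power if SDs are equal, with the caveat that it corrects only in part for skewed hold times.

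### Do the case-control label, and calling the explanatory factors dependent variables, require a change to the plan?

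*Combined protocol and SAP*

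**What the plan says.** The document is short and its sections are unnumbered.

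- **Methods paragraph, design label:** "It is a case control study, collecting both numerical and categorical data".
- **Methods paragraph, sample:** "48 (35 females, 13 males) healthy adults (aged 21–66 years) will perform 4 isometric core muscle endurance tests". No recruitment or eligibility text follows.
- **Methods paragraph, groupings:** first, "participants will be divided into 2 age groups considering the physiological changes taking place during aging", with the cut at 40 years; then "Participants will also be divided based on the physical activity level", according to whether activity guidelines are met.
- **Methods paragraph, analysis:** one sentence relates endurance to age, gender, back pain, activity and body mass index. On method, it says that this relation "is calculated using Pearson's correlation and Independent T-test on SPSS".
- **Opening statement:** the study will "investigate the core muscle endurance of different age groups and genders with all four endurance tests of the core".
- **Purpose paragraph:** the primary purpose is framed as a possible correlation between endurance and age. The secondary purpose is to "identify other dependent variables influencing isometric core muscle endurance", with low back pain, physical activity, gender and body mass index given as examples.

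**The concern.** A design label tells the reader how people came into the study. Case-control means that they were chosen by outcome status, which normally brings a case definition, a source of controls and often odds ratios. None of these appears here. A reader who took the label literally could misjudge the sampling, apply the wrong reporting standard, or look for a comparison of cases with controls that does not exist.

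The secondary purpose seems to reverse the roles of the variables. Something that influences endurance is explanatory, and endurance is the dependent variable. The word *other* places age in the same wrong class. The verb *influencing* also suggests a causal reading that two-variable tests in one observational sample cannot support. If these phrases steered the analysis, the wrong variable could be modelled as the outcome and the conclusions could be overstated.

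**Working it through.** The plan states no figure on this point to reproduce beyond the sample total, 35 + 13 = 48, which agrees. The check is whether either phrase determines anything that will be done.

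**1. The label against the described design.**

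| Feature | Case-control study | This plan |
|---|---|---|
| Selection | By outcome status | Not described |
| Groups | Cases and controls | Age (two groups); activity (two groups) |
| Variable defining the groups | The outcome | Explanatory factors |
| Outcome | Case status | Endurance on four tests, measured in everyone |
| Effect measure | Usually an odds ratio | Correlation or comparison of means |

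Outside the reference list, the words *case* and *control* each occur once, both in the label sentence. The plan does not say how the 48 people were found, so the label is unsupported by the text rather than contradicted by a stated sampling rule. The rest of the methods can be read without it. Everyone takes the same tests, and the results are related to personal characteristics. An analyst or reader would treat that as an observational, cross-sectional comparison if each person is tested once.

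**2. Whether the label feeds the analysis.** The analysis sentence lists five factors (age, gender, low back pain, activity level, body mass index) and relates each to endurance. With four tests that is 5 × 4 = 20 pairings. The methods are Pearson's correlation and the independent t-test. No odds ratio, matching or conditional analysis is named, so no planned step depends on case status. The second half of the label sentence notes that both numerical and categorical data are collected, which fits the two methods: correlation for numerical factors, t-test for two-group factors.

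**3. Whether the word *dependent* feeds the analysis.**

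- Pearson's coefficient is symmetric: r(X, Y) = r(Y, X). Naming age or endurance as dependent gives the same coefficient and p-value.
- For a two-group factor coded 0/1, the equal-variance t-test is a correlation test in another form: t = r√(n − 2) / √(1 − r²). With all 48 people contributing, the degrees of freedom are 48 − 2 = 46. Again, the role given to each variable does not enter.

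Pairings whose statistic or p-value would change if the word were corrected: 0 of 20.

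**4. Whether the intended meaning is in doubt.** The secondary purpose says that these variables influence endurance, which already makes them explanatory. The background presents endurance as something several factors may affect, age among them. The analysis sentence puts endurance on one side and all five factors on the other. The three places agree on the roles, and only the one word is wrong.

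**The case for a change.** The strongest argument for a correction is that the document is very short. With no recruitment or eligibility text, the label is the only statement about how people were sampled, and a reader has little else to correct it with. The usual rescues fail. Active versus non-active groups are defined by an explanatory factor, so they are not cases and controls. Low back pain could in principle define cases, and *healthy* does not rule this out, because the background uses that word for populations that include people with back pain. But the plan describes nobody as selected on back pain and lists it only as one of five correlates.

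It is also true that *influencing* claims more than unadjusted tests can show, and that the background leaves open whether weak endurance leads to back pain.

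So the label is poorly chosen, and conclusions should be limited to association. The argument does not show that anything planned is wrong. The primary purpose and the analysis sentence are already phrased as correlation. The absence of an adjusted analysis is a separate question about confounding, and rewording these sentences would not address it. Fixing the role of back pain as explanatory would settle a direction that the background leaves open, and the planned tests do not need that settled.

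**Conclusion.** Both observations about the wording are correct, and neither calls for a change to the plan. The case-control label is a misnomer that the methods do not support, and *dependent* is a slip whose meaning the next word makes plain. The size of the effect is nil: the same 48 people, the same four tests, the same two methods, and 0 of 20 results altered. A correction would reduce no bias, add no precision and leave the study's ability to answer its question unchanged.

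This rests on three assumptions. Participants were not in fact chosen by endurance or by back pain. Each person is assessed once, as the single set of tests suggests. The report describes its findings as associations, in line with the primary purpose. If people had been chosen by back pain, the missing item would be a description of the sampling, and the issue would go beyond a label. Nothing in the document indicates that. The two phrases can be tidied whenever the text is next edited or reported, but nothing depends on it.
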